5.3. Screening/Baseline/Run-in Failures

Screen failures are defined as subjects who consent to participate in the clinical trial but are never subsequently randomized. In order to ensure transparent reporting of screen failure subjects, meet the Consolidated Standards of Reporting Trials (CONSORT) publishing requirements, and respond to queries from Regulatory authorities, a minimal set of information about potential subjects who failed screening is required including demography, screen failure details, eligibility criteria, and SAEs.

5.3.1. Re-Screening

If a subject has not met all of the Eligibility Criteria within the 42-day screening period, re-screening is permitted. Subjects are only allowed to be re-screened once; the entire screening process must be repeated.

If a blood sample has to be redrawn due to sample handling problems, breakage or sample integrity, this is not considered a re-screening.

Further details regarding the procedure for re-screening may be found in the SRM.

5.3.2. Re-Testing

5.3.2.1. Laboratory Tests

If a subject fails any of the laboratory exclusion criteria, the test may be repeated twice within the screening period. If the subject fails the laboratory criteria for a third time they will be considered a screen failure; these subjects may be re-screened as described in Section 5.3.1.

If a blood sample has to be redrawn due to sample handling problems, breakage or sample integrity, this is not considered a re-testing.

Further details regarding the procedure for re-testing may be found in the SRM.

5.3.2.2. Pulmonary Function Tests

It is permitted to repeat the pulmonary function testing sessions (spirometry and/or D_{LCO}) once within the screening period, *i.e.* subjects may undergo a total of two D_{LCO} tests during the screening period).

If the screening D_{LCO} result is $\geq 60\%$ but <70% predicted, a chest HRCT must be performed. If this cannot be done within the screening window, then the subject must be re-screened.

5.3.2.3. Electrocardiogram (ECG) Test

The QTc is the QT interval corrected for heart rate according to Fridericia's formula (QTcF). The QTc should be based on average QTc values of triplicate ECGs obtained over a brief recording period (*e.g.*, 5-10 minutes).

The triplicate electrocardiogram (ECG) may be repeated once within the screening period if the recorded QTcF value was slightly out of range, and the Investigator does not consider that there are any other clinically-significant ECG abnormalities that would preclude the subject from participating in the study.

5.4. Withdrawal/Stopping Criteria

The following actions must be taken in relation to a subject who fails to attend the clinic for a required study visit:

- The site must attempt to contact the subject and re-schedule the missed visit as soon as possible.
- The site must counsel the subject on the importance of maintaining the assigned visit schedule and ascertain whether or not the subject wishes to and/or should continue in the study.
- In cases where the subject is deemed 'lost to follow up', the investigator or designee must make every effort to regain contact with the subject (where possible, three telephone calls and if necessary a certified letter to the subject's last known mailing address or local equivalent methods). These contact attempts should be documented in the subject's medical record.
- Should the subject continue to be unreachable, only then will he/she be considered to have withdrawn from the study with a primary reason of "Lost to Follow-up".

A subject may withdraw from study treatment at any time at his/her own request, or may be withdrawn at any time at the discretion of the investigator for safety, behavioral or administrative reasons. If a subject withdraws from the study, he/she may request destruction of any samples taken, and the investigator must document this in the site study records.

In addition, study medications will be discontinued and the subject withdrawn from the study in the event of any of the following:

- All serious infections.
- Pregnancy.
- Confirmed PAP (refer to Section 4.6.1).
- Severe or serious hypersensitivity reactions, including anaphylaxis.
- If the liver chemistry stopping criteria (Section 5.4.1) or QTc stopping criteria (Section 5.4.2) are met.
- Persistent or recurrent hematological laboratory abnormalities (see Section 5.5.2).
- Other serious or severe adverse events, at the discretion of the investigator, after consultation with the Medical Monitor.

If a subject withdraws from the study, he/she may request destruction of any samples taken, and the investigator must document this in the site study records.

Any subject who withdraws must complete an early withdrawal visit and the 12 week follow-up visit.

5.4.1. Liver Chemistry Stopping Criteria

Liver chemistry stopping and increased monitoring criteria have been designed to assure subject safety and evaluate liver event etiology (in alignment with the Food and Drug Administration (FDA) premarketing clinical liver safety guidance) [FDA, 2009].

5.4.1.1. Liver Chemistry Stopping and Increased Monitoring Algorithm

Liver Safety Required Actions and Follow up Assessments Section can be found in Appendix 12.3.

5.4.1.2. Study Treatment Restart or Rechallenge

Study treatment restart or rechallenge after liver chemistry stopping criteria are met by any subject participating in this study is not allowed.

5.4.2. QTc Stopping Criteria

The same QT correction formula must be used for each individual subject to determine eligibility for and discontinuation from the study. The QTc correction formula to be used is the QT interval corrected for heart rate according to Fridericia's formula (QTcF). This formula may not be changed or substituted once the subject has been enrolled.

For example, if a subject is eligible for the protocol based on QTcF, then QTcF must be used for discontinuation of this individual subject as well.

Once the QT correction formula has been chosen for a subject's eligibility, the same formula must continue to be used for that subject for all QTc data being collected for data analysis. Safety ECGs and other non-protocol specified ECGs are an exception.

The QTc should be based on a single QTc value. The QTc is the QT interval corrected for heart rate according to Fridericia's formula (QTcF).

• The ECG may be repeated in triplicate if the recorded QTcF value is out of range. The QTc should then be based on averaged QTc values of the triplicate ECGs obtained over a brief recording period (*e.g.*, 5-10 minutes).

A subject who meets either of the bulleted criteria below will be withdrawn from the study:

a. QTc >500 msec OR uncorrected QT >600 msec

b. Change from baseline of QTc >60 msec

The QTc is the QTcF.

For subjects with underlying **bundle branch block**, follow the discontinuation criteria listed below:

Baseline QTc with bundle branch block	Discontinuation QTc with bundle branch block
<450 msec	>500 msec
450 – 480 msec	≥530 msec

5.5. Treatment Interruption

5.5.1. Respiratory Symptoms

Study medications will be temporarily suspended to allow investigation in the event of any of the following:

• Persistent cough (common terminology criteria (CTC) grade 2 or 3) or dyspnea (Borg scale grade 3 or above) for three consecutive weeks. Details on CTC and Borg scale are provided in the SRM.

The subject should be referred to a pulmonologist for further assessment. The study drug should be suspended until the symptoms or signs that caused the referral have resolved and/or the diagnosis has been determined and clinically significant events have been excluded by the pulmonologist. As described in Section 5.4, a confirmed diagnosis of PAP necessitates permanent cessation of study medication and withdrawal of the subject from the study. Suggested pulmonary assessment and management algorithms are provided in a separate Pulmonary Safety Guidance Document in the SRM.

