	 A recent study has reported that individual auto- antibodies from patients only partially-neutralized GM-CSF and when injected into mice together with human GM- CSF led to the accumulation 	Number 2014N190256_01) for further details). Therefore, the risk of development of PAP in this study is anticipated to be low.
	CSF led to the accumulation of a large pool of circulating GM-CSF that remained partially bioavailable [Piccoli, 2015]. In contrast, a combination of three non- cross-competing antibodies completely neutralized GM- CSF activity in vitro by sequestering the cytokine in high-molecular-weight complexes, and in vivo promoted the rapid degradation of GM-CSF- containing immune complexes in an Fc-	 Subject Monitoring: Specific pulmonary assessments are a requirement of the study protocol: Subjects will be assessed every visit for the development of cough and dyspnea, and will also have regular chest auscultation and pulse oximetry measurements. Persistent cough or
	dependent manner. These findings provide a plausible explanation for the severe phenotype of PAP patients and for the low likelihood of treatments based on single anti-GM-CSF monoclonal antibodies causing PAP.	 dyspnea will be reported as an AESI. Pulmonary function testing (spirometry and D_{LCO} measurements) will be performed during screening, at 12 weeks, and at the follow-up visit. Relative
	Non-clinical Data: Non-adverse minimal to mild foamy alveolar macrophage accumulation was noted in lungs of monkeys in the 13-week SC and 26-week intravenous (IV) toxicology studies, but reversed following off drug period. Dose levels at which foamy alveolar macrophages were not	 decrease in D_{LCO} >15% from screening will be reported as an AESI if confirmed with three consecutive weekly tests. In the event of any new or clinically significant pulmonary abnormalities that may develop during the

Potential Risk of Clinical	Summary of Data/Rationale	Mitigation Strategy
Significance	for Risk	

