Potential Risk of Clinical Significance	Summary of Data/Rationale for Risk observed were identified in these studies. Clinical Data: No cases of PAP have been reported to date in the clinical development program. Furthermore evaluation of pulmonary function has not demonstrated any abnormalities in pulmonary functions.	Mitigation Strategy study and persist for three consecutive weeks (e.g. , increased shortness of breath/dyspnea, or unexplained and persistent coughing), the subject will be withdrawn from study drug for the remainder of the study and it is recommended that the subject be referred to a pulmonologist for further assessment. The subject should be followed until the symptoms or signs that caused referral have
		resolved and/or the diagnosis has been determined. Suggested pulmonary assessment and management algorithms will be provided in a separate Pulmonary Safety Guidance Document in
Hypersensitivity reactions, including anaphylaxis	There is a potential risk of hypersensitivity reactions, including anaphylaxis, during and following the administration of protein-based products, such as GSK3196165. Clinical Data: No allergic or acute systemic reactions have been observed to date in the clinical development program.	 Subject Selection: Subjects with a history of sensitivity to any of the study treatments, or components thereof, or a history of drug or other allergy that, in the opinion of the investigator or Medical Monitor, contraindicates their participation, will not be permitted to enter the study.
		Study Treatment Administration/Subject

Summary of Data/Rationale	Mitigation Strategy
for Risk	
	 Monitoring: All SC administrations will be performed at the clinical site. Subjects will be required to remain monitored at the site for 1 hour after the injection for the first three injections, and then for 30 minutes for subsequent injections. Subjects should be informed of the signs and symptoms of an acute hypersensitivity reaction, and be instructed to seek immediate medical care should they develop. This information will also be contained within the subject Informed Consent Form. Should hypersensitivity or anaphylaxis occur, subjects should be managed appropriately per local guidelines/medical judgment. Severe or serious hypersensitivity or anaphylaxis is categorized

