12.9. Appendix 12.9 - Protocol Changes

Protocol Amendment: 01 (applies to all countries)

Section 1. Protocol Synopsis for Study 205180 and Section 3. Objectives and Endpoints.

Classified primary and secondary objectives and endpoints.

Rationale

Previous version listed all objectives and endpoints as exploratory.

Section 1. Protocol Synopsis for Study 205180, Section 4.1. Overall Design, Section 5.3 .1. Re Screening, Section 7.1. Time and Events Table, and Section 7.2. Screening and Critical Baseline Assessments

Screening window extended to six weeks.

Rationale

To facilitate scheduling of screening MRI scan, which should only be performed after other screening assessments have been passed.

Section 4.3. Type and Number of Subjects

Estimated number of screened subjects revised.

Rationale

More conservative estimate based on recent clinical study experience.

Section 4.6.1. Risk Assessment

Deleted ">15% relative decrease in D_{LCO} from screening" as trigger for subject to be withdrawn from study drug.

Rationale

Second D_{LCO} test is at Week 12, after dosing of study drug has been completed.

Section 5.1. Inclusion Criteria, Section 5.3.2.2. D_{LCO} test, Section 7.1. Time and Events Table, Section 7.2. Screening and Critical Baseline Assessments, and Section 7.6.12. Pulmonary Assessments

Consolidated details of PFTs into additional guidance in Section 7.6.12.

Rationale

To avoid any misunderstanding of PFTs.

Section 5.1. Inclusion Criteria

Addition of Day 1 joint count, and clarification that chest HRCT must be performed if $D_{LCO} \ge 60\%$ - <70% predicted.

Rationale

To ensure subjects still have active RA with the extended screening window, and to avoid any misunderstanding of requirement for chest HRCT.

Section 5.2. Exclusion Criteria

Addition of history of sensitivity to Gd-containing contrast agents.

Rationale

To maintain safety.

Section 5.3.1.Re-Screening

Re-screening is permitted.

Rationale

Had previously stated that re-screening is required.

Section 7.1. Time and Events Table

Revision that subjects must have passed all screening assessments, including laboratory tests, prior to undertaking MRI scanning, and that whole blood flow cytometry is scheduled at Baseline (Day 1).

Rationale

It is more appropriate that these tests are done for patients likely to be randomized.

Section 7.1. Time and Events Table and Section 7.2 Screening and Critical Baseline Assessments

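### For new, unexplained cough or dyspnea at the Section 5.5.1 grades lasting three weeks, Section 4.6.1 ends dosing for good while Section 5.5.1 only pauses it

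*Protocol*

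**What the plan says.** Protocol Section 5.5.1 sits under the heading on treatment interruption. It states "Study medications will be temporarily suspended to allow investigation in the event of any of the following" and lists cough of CTC grade 2 or 3 "or dyspnea (Borg scale grade 3 or above) for three consecutive weeks". The subject is to see a pulmonologist. The pause has an end point: "The study drug should be suspended until the symptoms or signs that caused the referral have resolved and/or the diagnosis has been determined", with clinically significant events excluded by the pulmonologist. The section reserves permanent cessation for confirmed PAP.

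The PAP row of the Section 4.6.1 risk table has its own rule. It opens "In the event of any new or clinically significant pulmonary abnormalities that may develop during the" and continues, across a table break, "study and persist for three consecutive weeks". Its examples are increased breathlessness and unexplained, persistent coughing. The action is that "the subject will be withdrawn from study drug for the remainder of the study", with referral to a pulmonologist recommended.

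Two other sections bear on the point. The only specifically respiratory entry in the Section 5.4 withdrawal list begins "Confirmed PAP (refer to Section 4.6.1". Section 7.6.12 advises referral and suspension, until resolution and/or diagnosis and exclusion of significant events, for new or clinically significant pulmonary abnormalities. It sets no grade and no minimum duration.

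**The concern.** Both rules are mandatory in wording, both act at three consecutive weeks, and both cover cough and dyspnea. One ends dosing for good; the other pauses it and lets it resume. The protocol gives no order of precedence, and Section 7 does not allow waivers except for immediate safety concerns.

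At stake is the handling of individual subjects for a risk that the protocol itself takes seriously: Section 4.6.3 names pulmonary toxicity among the key potential risks, and Section 7.6.12 treats lung assessments as central to safety monitoring. One site could restart dosing after clearance and another could stop permanently for the same presentation, each following the protocol.

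**Working it through.** The protocol states no figure to reproduce. The check is a comparison of texts, followed by a dose count.

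**Side by side, for a subject with new, unexplained grade 2 cough for three weeks**

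| Section | Condition met? | Action | Restart |
|---|---|---|---|
| 4.6.1 | Yes: new, persistent, three weeks | Off study drug for the rest of the study | No |
| 5.5.1 | Yes: grade 2, three weeks | Temporary suspension and referral | Implied after resolution and/or diagnosis and clearance |
| 7.6.12 | Yes: new abnormality, no minimum duration | Suspension advised | Implied, on the same terms |
| 5.4 | No, unless PAP is confirmed | None | Not addressed |

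The Section 5.4 list pairs stopping drug with leaving the study, so its silence supports 5.5.1 but is not decisive.

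Restart in 5.5.1 is an inference from the temporary nature of the suspension and its stated end. The protocol is explicit elsewhere: Section 5.4.1.2 forbids restart after a liver stopping event, and Section 5.5.2 gives both restart and permanent-stop conditions for hematologic abnormalities.

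**Dose count**

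Inputs: doses of 180 mg (Section 4.5.1) on Days 1, 8, 15, 22, 29, 43, 57 and 71, with later visits on Days 85 and 155 (Section 7.1). Total: 8 × 180 = 1,440 mg.

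Let d be the scheduled visit at which the symptom is first recorded. The trigger visit t is the first scheduled visit with day ≥ d + 21. The dose at t is withheld under both rules, so the rules differ only for doses after t, and fully only if clearance comes before the next dose.

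| d | d + 21 | t | Doses after t | mg | Share of 1,440 mg |
|---|---|---|---|---|---|
| 8 | 29 | 29 | 43, 57, 71 (three) | 540 | 37.5% |
| 15 | 36 | 43 | 57, 71 (two) | 360 | 25% |
| 22 | 43 | 43 | 57, 71 (two) | 360 | 25% |
| 29 | 50 | 57 | 71 (one) | 180 | 12.5% |
| 43 or later | 64 or later | 71 or later | none | 0 | 0% |

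The count depends on how three weeks is read. If it means the third consecutive weekly assessment, t = d + 14, and the schedule supplies such a run only for d = 8 (Days 8, 15, 22) and d = 15 (Days 15, 22, 29). The doses after t are then four (29, 43, 57, 71; 720 mg, 50%) and three (43, 57, 71; 540 mg, 37.5%).

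**The case against.** The strongest reply is that little turns on this in practice. At the 5.5.1 grades both rules stop dosing at three weeks and both look to a pulmonologist. Confirmed PAP is a permanent stop in any case, the investigator may withdraw a subject at any time for safety (Section 5.4), and the sponsor's safety team reviews blinded data about monthly (Section 4.6.3). Sections 5.4, 5.5.1 and 7.6.12 agree, and 4.6.1 could be taken as a background table. Most of this stands, and it is why the point is minor.

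The last step does not stand. Section 5.4 refers to 4.6.1 for PAP. Amendment 01 removed the DLCO decrease from 4.6.1 "as trigger for subject to be withdrawn from study drug", because the second DLCO test comes after dosing has ended. The sponsor therefore treated that sentence as an operative dosing rule and left it in force for the other abnormalities. Nor does the Pulmonary Safety Guidance Document settle the matter: it is not shown, and the protocol calls its algorithms only suggested.

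Three stronger readings are tempting, and the documents do not support them.

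- A reader might infer that 4.6.1 ends dosing for cough or dyspnea at any grade. It states no grade, but its terms are new or clinically significant, and its cough example is unexplained.
- A reader might infer that the restart in 5.5.1 can never be used. A grade 2 cough with an identified cause meets 5.5.1 while arguably falling outside 4.6.1, so the overlap is large but not shown to be total.
- A reader might see a second conflict for symptoms below the 5.5.1 grades. Section 7.6.12 already advises suspension for such symptoms, so what remains is largely the same restart question.

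**Conclusion.** The contradiction is real and stands in current text, within stated limits: new, unexplained cough of CTC grade 2 or 3, or dyspnea of Borg 3 or above, lasting three consecutive weeks. Section 4.6.1 is the outlier.

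For symptoms first recorded on Day 8, up to three of eight doses differ. This assumes the trigger falls at the first scheduled visit at least 21 days later, doses are on nominal days, and clearance comes before Day 43. The difference shrinks to none for first recording on Day 43 or later. The protocol gives no rate of three-week cough or dyspnea, so the number affected cannot be estimated; with about 40 subjects randomized 3:1 (about 30 on active drug), few are likely.

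A reader might go on to infer bias in the study's results. Nothing in the protocol supports that. Severity is minor: a wording inconsistency in a safety rule that should be aligned.

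**What to change.** Replace the action sentence in Section 4.6.1 with a cross-reference to Section 5.5.1. Add one sentence to 5.5.1 saying that dosing may restart only after pulmonologist clearance, and that confirmed PAP remains a permanent stop with withdrawal from the study.

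If the sponsor's medical team intends a permanent stop at three weeks, it should instead amend 5.5.1 to say so and add the trigger to the Section 5.4 list.

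The cost is a few lines of protocol text and any matching lines in the Pulmonary Safety Guidance Document. Each choice has a downside. Under restart, a subject whose early lung signal was missed could be re-exposed, which is why clearance should be a condition. Under a permanent stop, a subject with a benign cause loses the later doses counted above.

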5.5.2. Hematologic Abnormalities

The following hematological laboratory abnormalities require temporary suspension of study medications and prompt retesting, ideally within 3-5 days:

- White blood cell count $<2.0 \times 10^9/L$
- Absolute neutrophil count $<1.0 \times 10^9/L$
- Lymphocyte count $<0.5 \times 10^9/L$

Study medication should not be restarted until the parameters are above these values, and subjects should be followed as appropriate until resolution of the event.

If these abnormalities are persistent (present on \geq two sequential tests), or occur recurrently (on two separate occasions), study medications will be permanently discontinued and the subject withdrawn from the study.

5.6. Subject and Study Completion

A completed subject is one who has completed all phases of the study including the follow-up visit.

The end of the study is defined as the last subject's last visit.

6. STUDY TREATMENT

6.1. Investigational Product and Other Study Treatment

The term 'study treatment' is used throughout the protocol to describe any combination of products received by the subject as per the protocol design. Study treatment may therefore refer to the individual study treatments or the combination of those study treatments.

	Study Tr	Co-medication	
Product name:	GSK3196165	Placebo	Methotrexate and folic (or
			folinic) acid.
Function:	Test (study	Control	Background treatment
	treatment)		(started prior to and
			maintained during the
			study).
Formulation	See IB (GSK	Sterile 0.9%	Variable. See labels for
description:	Document Number	(weight/volume	details.
	2014N190256 01	[w/v]) sodium	
) for details.	chloride solution.	
Dosage form:	Liquid	Liquid	MTX: tablet or liquid
_	-		Folic (or folinic) acid:
			capsule, tablet or liquid.

	Study Tr	eatment	Co-medication			
Dosage levels	180 mg (1.2mL)	1.2 mL	MTX:7.5-25 mg/week			
(volumes):			Folic (or folinic) acid:			
, ,			≥5 mg/week.			
			Note: Folic (or folinic) acid			
			dose may be increased to			
			counteract side-effects of			
			MTX (including nausea.			
			mucositis, and headache).			
			Refer to Inclusion			
			criterion 6 in Section 5.1.1			
Route of	Study treatment shou	ld be administered	MTX [·] oral or subcutaneous			
Administration	SC into thigh or abdo	men sites should be	injection			
	rotated Safety shoul	d be monitored for				
	1 hour after the inject	ion for the first	Folic (or folinic) acid: oral			
	3 injections then for 3	30 minutes				
	thereafter Such mor	nitorina will include				
	general safety monito	rina includina				
	monitoring for system	ic hypersensitivity				
	infusion reactions and	local injection site				
	reactions. Trained re	scue personnel and				
	rescue medications/e					
	available for use at al					
Dosing instructions:	GSK3196165/placebo	MTX: can be taken as a				
	administered on the s	ame dav each week	single weekly dose, or			
	± 1 day for the first five	/e weekly doses	divided weekly dose, per			
	(with a minimum of 5	davs between	investigator's discretion.			
	doses, for no more th	an two consecutive	Folic (or folinic) acid			
	doses). Following thi	should be taken the day				
	GSK3196165/placebo	after and at least 12 hours				
	administered on the s	following MTX				
	week (EOW) ± 3 day	administration.				
	8 days between dose					
	Every attempt should	be made to ensure				
	all doses are adminis	tered.				
Physical description:	Sterile, aqueous	Sterile 0.9% (w/v)	See label for details.			
	solution of purified	sodium chloride				
	monoclonal	solution. See label				
	antibody	for details.				
	150 mg/mL					
Method for	180 mg dose -	A volume of 1.2 mL	See label for details.			
individualizing	required volume will	will be drawn into a				
dosage:	be drawn into a	small (e.g. 2 or				
	small (e.g. 2 mL or	3 mL) syringe.				
	3 mL) syringe.	_				
	The required					
	volume should be					
	dosed immediately.					

Investigators are responsible for ensuring that subjects continue to receive MTX and folic acid.

Timing of MTX is unrelated to food intake, and may be changed at the investigator's discretion in case of intolerability.

Subjects will receive ≥ 5 mg/week folic (or folinic) acid orally. The dosing regimen is at the discretion of the investigator. Folic (or folinic) acid should be taken the day after MTX administration and at least 12 hours following the MTX. Folic (or folinic) acid dose may be increased to counteract side-effects of MTX (including nausea, mucositis, and headache).

MTX dosing should be kept stable throughout the study as far as possible. Dose reduction is permitted to a minimum of 7.5 mg/week due to intolerance or toxicity, and dose increase, following reduction, is permitted back to the subject's dose at the entry into study (maximum dose 25 mg/week). Likewise, temporary interruption of MTX dosing for the management of intolerance will be permitted, and any reduction or interruption should be recorded, with the reason, in the electronic case report form (eCRF).

All local standard-of-care practices for the administration of MTX, including laboratory testing, follow-up care, contraindications, and folic acid administration should be performed throughout the study.

